#### Self-Weighing (Certain Loss)

Participants randomized to an arm that contains the self-weighing (certain loss) component will have a balance shown at the beginning of the study on the participant dashboard and each day that they do not weigh, \$0.50 will be subtracted from this account. The beginning balance will be based on the number of days until 36 weeks gestation for each participant, which will vary slightly due to when participants enroll in the study. Participants will receive their weekly payout (a maximum of \$3.50 for 7 days) from weigh-in on Mondays of the following week. A maximum of \$112 could be earned over the pregnancy.

#### Monthly GWG component

Participants randomized to an arm that contains the monthly GWG incentive component will receive \$14 per month if they have gained within the recommended monthly range for their BMI category (Table 2). "Ineligible for incentive" participants will be specifically notified that

they would have received \$14 had they had gained within the recommended range for the month, drawing on research showing that loss aversion can be motivating. Participants will receive their monthly balance on the first weekday of the following month. A maximum of \$112 could be earned over the pregnancy.

Table 2. Monthly weight gain goals by weight status

		Monthly Weight Gain Goals		
		Normal Weight	Overweight	Obese
1st Trimester	Week 5-8	< 2.2 lbs	< 2.2 lbs	< 2.2 lbs
	Week 9-12	< 2.2 lbs	< 2.2 lbs	< 2.2 lbs
2nd Trimester	Week 13-16	2 - 4.4 lbs	1 - 3 lbs	1 - 2.2 lbs
	Week 17-20	2 - 4.4 lbs	1 - 3 lbs	1 - 2.2 lbs
	Week 21-24	2 - 4.4 lbs	1 - 3 lbs	1 - 2.2 lbs
3rd Trimester	Week 25-28	2 - 4.4 lbs	1 - 3 lbs	1 - 2.2 lbs
	Week 29-32	2 - 4.4 lbs	1 - 3 lbs	1 - 2.2 lbs
	Week 33-36	2 - 4.4 lbs	1 - 3 lbs	1 - 2.2 lbs

#### Overall GWG component

Participants randomized to an arm that contains the overall GWG incentive component will be given the Institute of Medicine gestational weight gain recommendation based on their body mass index at randomization, adjusted for data collection at 36 weeks (Table 3). If they achieve the goal at 36 weeks, they will receive \$112 after the data collection visit.

Table 3. Overall weight gain goals by weight status (adjusted goals based on data collection at 36 weeks gestation)

Table 3. Overall weight gain goals by weight status (adjusted goals based on data collection at 36 weeks gestation)			
	Normal Weight	Overweight	Obese
Overall Weight Gain	21-31 lbs	13-23 lbs	9-18 lbs

#### Weekly physical activity

Participants randomized to an arm that contains the physical activity component will be asked to achieve a 150 minute physical activity goal for each week based on the guideline from the American College of Obstetricians and Gynecologists (ACOG), 21 and they will receive \$3.50 if they meet their activity goal for the week. Participants who do not meet the activity goal will be notified that they would have received \$3.50 had they met their activity goal, drawing on research showing that loss aversion can be motivating. Participants will receive their weekly payout on Mondays of the following week.

The total amount that any one participant can earn through the incentives is \$336.

Measures will be obtained by trained research staff who are blinded to treatment assignment and who will be located within the obstetric clinic. Baseline measures will be obtained just prior

to randomization. In-person follow-up data collection visits will be scheduled at gestational week 32 and week 36. Incentives (\$30 for each follow-up visit) will be used to obtain high retention at all follow-up data collection visits. In addition, the research staff will attempt to schedule the data collection visits before or after regular office visits, in order to facilitate retention.

## 5. Study/Project Procedures

- a. recruitment
- b. randomization into study arms
- c. participants receive feedback about whether their numbers were drawn in the lottery and whether they won the incentive pending weight management results
- d. study team analyzes whether different incentive structure affects participants' gestational weight gain

## 6. Outcome Measures

**Intervention Satisfaction:** At 32 weeks gestation, participants will be asked to offer insight into program acceptability in each condition, as well as satisfaction to the program in general. We will examine feedback on specific intervention aspects, which will inform program refinement and future implementation.

**Recruitment yields observed from enrollment survey:** The number of participants initially recruited for the study will be closely monitored.

**Program retention observed from enrollment and follow-up surveys:** The number of participants stayed in the study within the time frame of the study will be closely monitored.

**Gestational Weight Gain** (i.e., baseline to final prenatal visit): At all measurement visits, weight will be recorded in kilograms on a calibrated research-grade scale. Weight will be measured on a calibrated digital scale in duplicate, with the participant wearing light clothing and no shoes. While we will obtain the mother's weight at baseline, we will also obtain self-reported preconception weight (before the last menstrual period). We will calculate the participant's GWG goal based on self-reported preconception BMI. Strong concordance between self-reported preconception weight and measured pregravid weight has been demonstrated. The difficulty of anticipating when a final weight should be obtained to capture the fullest extent of GWG was considered, and we elected to use an approach that afforded two possible weights that would be available for analytic purposes. The Week 36 weight will be the primary outcome except for mothers who deliver prior to 36 weeks, in which case we will use the Week 32 weight. Thus, we will have a final observation of GWG for all participants, regardless of whether they deliver earlier than 36 weeks. However, only approximately 11% of pregnant women have their child before 37 weeks; thus, we expect that we will be able to collect Week 36 data on most participants.

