## 3. Study/Project Population

There will be 50 mother and baby pairs (N=100) included to account for screening failures but only 40 of those pairs (N=80) randomize. Pregnant participants (N=100) in their first trimester at an OB-GYN Specialists clinic in Memphis, TN will be randomized in a fractional factorial experiment. Participants must be at least 18 years old and be less than 12 weeks gestation upon recruitment (based on the date of their last menstrual period and then confirmed by their physician at their first prenatal visit), as interventions that begin prior to gestational week 12 are more effective.

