their eligibility (i.e. whether participants are 18 years or older, whether they are no more than 12 weeks pregnant, and whether they have wireless internet or a Bluetooth connected device). Eligible participants will first answer a few questions about the number of pregnancies they have prior to the current one, age, annual household income, marital status, employment status, household size, education level, race, and ethnicity. Then, they will be randomized to one of the study arms and led through an automated description of the details specific to that arm. Participants will be provided with details regarding how to contact the research team via email or phone at any time if they subsequently wish to withdraw from the study. This contact information will remain easily accessible via the participants' individual Way to Health web portal dashboards throughout the study.

Participants (N = 40) will be randomized to one of 8 conditions , with combinations of 3 different components of incentive for GWG management and physical activity. Assessments will be conducted at baseline (i.e., in the first trimester), 32 weeks gestation and 36 weeks gestation (if the participant has not yet delivered) and will include measures of body weight and treatment satisfaction. Participants will be asked to complete daily weigh-ins using the scale provided by the study, as well as wear a physical activity tracker (i.e. Fitbit).

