### **Analysis Plan**

This is a feasibility study, the primary purpose of which is to gather data that would evaluate the feasibility of recruitment, randomization, and retention, as well as treatment engagement and intervention satisfaction. An additional aim of this study is to pilot the intervention components, consistent with the preparatory stage of the multiphase optimization strategy framework. The trial was not powered to detect a significant difference among the conditions on treatment engagement or GWG.

We will describe characteristics of the sample using counts and percentages for categorical data and means and SDs for continuous data. All analyses will be implemented using R (version 4.0.2; The R Foundation for Statistical Computing).

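### The only subgroup the plan names for acceptability is the condition (about 5 women each); no summary by component level is specified, although piloting the components is a stated aim

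*Combined protocol and SAP*

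**What the plan says.** **Design.** Section 4 (Research Design) states: "Participants (N = 40) will be randomized to one of 8 conditions", "with combinations of 3 different components of incentive for GWG management and physical activity". Section 3 (Study/Project Population) says that women "will be randomized in a fractional factorial experiment".

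**Acceptability.** Under Intervention Satisfaction in section 6, at 32 weeks, "participants will be asked to offer insight into program acceptability in each condition". The same paragraph also covers satisfaction with the programme as a whole and comments on particular parts of the intervention. It gives no grouping or denominator for those comments.

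**Engagement.** The Other Measures list names daily self-weighing and weekly active minutes as engagement measures, with no grouping.

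**GWG.** Section 5 (Study/Project Procedures), item d, plans to examine whether incentive structure affects GWG, without naming the unit of comparison.

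**Analysis Plan.** The primary purpose is feasibility, including engagement and satisfaction. It adds: "An additional aim of this study is to pilot the intervention components". Its only reference to a between-group difference is a disclaimer: "The trial was not powered to detect a significant difference among the conditions on treatment engagement or GWG". The one analysis it specifies is a description of the sample by counts, percentages, means and SDs. No confidence intervals are mentioned.

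**The concern.** In a factorial design every woman informs every component, so a component level pools several conditions. The only subgroup this plan names is the single condition, which is the smallest and least precise one available.

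Section 6 says that what women report will feed into refinement and later implementation. A percentage from about 5 women, shown without an interval, is easily over-read. The same data grouped by component level would describe each component with more women and would serve the stated aim directly. For engagement and GWG the gap is different: no unit of summary is given, so the choice is left until the data are in.

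**Working it through.** The document gives no precision, power, per-condition or per-level figure to reproduce. Its one checkable figure on the component structure is the incentive cap.

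**1. Component structure**
- Section 4 gives stated maxima of $112 each for lottery, certain loss and monthly GWG, and a single payment of $112 for overall GWG.
- No maximum is stated for activity. The certain-loss maximum implies 112 / 3.50 = 32 weeks; the same 32 weeks at $3.50 gives $112 for activity.
- The cap for any one woman is $336 = 3 x $112, so three components each.
- This fits three two-level components: self-weighing (lottery or certain loss), GWG (monthly or overall) and activity (present or absent). Then 2 x 2 x 2 = 8 conditions.
- The layout is inferred. The text available shows no table of the 8 conditions and no allocation ratio. Eight conditions from three two-level components would be a full factorial, whereas section 3 calls the design fractional. Any balanced two-level design in 8 conditions places each level in 4 of them.

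**2. Women per group** (equal allocation assumed)
- Per condition: 40 / 8 = 5.
- Per level present in k of the 8 conditions: 5k. So k = 4 gives 20, k = 3 gives 15 and k = 2 gives 10.
- A condition is therefore 1/4, 1/3 or 1/2 of a level.
- Section 3 says both that "only 40 of those pairs (N=80) randomize" and that 100 pregnant participants will be randomized. I use 40, as section 4 does. The ratios do not depend on the total.

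**3. Precision for a proportion** (exact Clopper-Pearson 95% interval; 80% is illustrative)

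| Group | Count | 95% CI |
|---|---|---|
| One condition | 4/5 | 28% to 99% |
| Level in 2 conditions | 8/10 | 44% to 97% |
| Level in 3 conditions | 12/15 | 52% to 96% |
| Level in 4 conditions | 16/20 | 56% to 94% |
| All women | 32/40 | 64% to 91% |

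If every woman finds the programme acceptable, the lower limit is 0.025^(1/n): 48% for 5/5 and 83% for 20/20.

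**4. Precision for means, in SD units**
- Half-width of a 95% CI for one mean, t(0.975, n-1) / sqrt(n): 1.24 SD at n = 5 and 0.47 SD at n = 20.
- Standard error of a difference, sqrt(2/n): sqrt(2/5) = 0.63 SD for 5 versus 5, and sqrt(2/20) = 0.32 SD for 20 versus 20.

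**5. Attrition.** Women lost before week 32 shrink both counts. At an assumed 80% retention they become 4 and 16, and the ratio is unchanged.

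**The case against.** The strongest reply is that the plan does not contain a condition-level analysis to criticise. Much of this stands.

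- **Engagement and GWG.** A reader might infer that these too will be estimated condition by condition, so that every estimate uses a quarter of the women available. The document does not support that. Engagement has no stated grouping, the disclaimer on power rules out a comparison rather than specifying one, and section 5 speaks of incentive structure, not of eight cells.
- **Acceptability.** The sentence describes what women are asked, and collecting answers by condition does not prevent pooling later. Section 6 also covers the programme as a whole, which uses all responders, and comments on parts of the intervention, which may well mean components. But no grouping is given for those comments, so they do not supply a component-level summary.
- **Component selection.** A reader might infer that this pilot decides which components go forward. The document says only that feedback informs refinement and future implementation, and piloting components is an additional aim.
- **Twenty per level.** This is an assumption. Other layouts give 10 or 15, still two to three times a single condition.

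That this is an unpowered pilot does not answer the point. Nothing here asks for tests, power or more women. Engagement and satisfaction fall within the primary purpose, so how they are summarised matters even without a comparison.

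**Conclusion.** The point holds in a limited form. The plan names the condition (about 5 women) as a unit for acceptability, leaves the unit for engagement and GWG unstated, and specifies no summary by component level despite its aim of piloting components.

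Under equal allocation and balanced two-level components, a level has four times as many women as a condition and the standard error of a mean difference is halved. If a level is present in only 2 or 3 conditions, it has two or three times as many. The 80% acceptability is illustrative and not a figure from the plan.

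This is a cheap improvement to how data already being collected are reported. It is not a flaw that undermines the feasibility aims.

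**What to change.** In section 6 and the Analysis Plan:

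1. Report feasibility proportions (recruitment, randomization, retention) for the whole sample, with exact 95% confidence intervals.
2. Summarise acceptability, self-weighing, active minutes and GWG descriptively by level of each component. Use exact 95% intervals for proportions of women and 95% intervals for means or mean differences. Reduce self-weighing to one figure per woman (share of days weighed) first, so that days are not counted as independent observations.
3. Show the 8-condition table as a listing only.
4. State the 8 conditions, the levels of each component and the allocation ratio, so that the number per level can be read off.
5. State that component contrasts are descriptive and not powered and, if the design is a fraction, that they are aliased with interactions.

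The cost is wording and a few table shells, with no added women or visits. The downside is that component averages can mask an interaction, but about 5 women per condition could not show one anyway.

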## *Other Measures*

**Height:** Height will be recorded in centimeters.

**Demographics:** Participants will complete a questionnaire regarding their age, annual household income, marital status, employment status, education level, race, and ethnicity.

**Weight Self-Monitoring:** We will electronically monitor daily self-weighing as a measure of treatment engagement (coded each day as present or absent).

**Physical Activity:** We will electronically monitor participants' weekly physical activity as a measure of treatment engagement (measured in active minutes).

### **Analysis Plan**

This is a feasibility study, the primary purpose of which is to gather data that would evaluate the feasibility of recruitment, randomization, and retention, as well as treatment engagement and intervention satisfaction. An additional aim of this study is to pilot the intervention components, consistent with the preparatory stage of the multiphase optimization strategy framework. The trial was not powered to detect a significant difference among the conditions on treatment engagement or GWG.

We will describe characteristics of the sample using counts and percentages for categorical data and means and SDs for continuous data. All analyses will be implemented using R (version 4.0.2; The R Foundation for Statistical Computing).
